2.4.1.1 Duration of exposure

The duration of exposure (in months) will be summarized for study treatment (combination) and for each study drug individually (sabatolimab, azacitidine and venetoclax) based on summary statistics and categorical analyses (e.g. exposure <1 month, at least 1 month, at least 2 months etc.). Details on start and end dates used for derivations are outlined in Appendix Section 4.

2.4.1.2 Cumulative dose

For sabatolimab, the actual cumulative dose in mg is the sum of "dose administered" from the eCRF of all cycles during the exposure to sabatolimab.

For azacitidine, the actual dose in mg/m^2 in each cycle is the "dose administered" in mg during that cycle divided by the body surface area (BSA) at the beginning of the cycle using the weight measured before the infusion at that cycle. If the weight is not collected at the beginning of the cycle, the weight from the previous visit will be considered. The actual cumulative dose in mg/m^2 is then the sum of all cycles. The following formula (Mosteller) is used for BSA:

$BSA(m^2) = \sqrt{Weight(kg) * Height at screening(cm)/3600}$

For venetoclax, the actual cumulative dose in mg is the sum of "dose administered" from the eCRF of all cycles during the exposure of venetoclax.

2.4.1.3 Dose intensity and relative dose intensity

Dose intensity is defined for participants with non-zero duration of exposure. For participants who did not take the drug, the dose intensity is by definition equal to zero. The actual dose intensity (computed as the ratio of actual cumulative dose received and duration in days from first to last cycle initiated) and the relative dose intensity (computed as the ratio of actual dose intensity and planned dose intensity) will be summarized for each study treatment component by descriptive statistics. The planned dose intensity for each of the study treatment components is the ratio of planned cumulative dose and duration in days from first to last cycle initiated:

- Sabatolimab: the planned dose intensity is 400 mg/28 days or 800 mg/28 days,
- Azacitidine: the planned dose intensity is 75 mg/m²/day which is equivalent to 525 mg/m²/28 days,
- Venetoclax: the planned dose intensity is 400 mg/day which is equivalent to 5600 mg/28 days when the recommended full daily dose of venetoclax is 400 mg.

The relative dose intensity is then computed as the ratio of actual dose intensity and planned dose intensity. For example, if a participant received sabatolimab at 600 mg Q4W on average throughout the study (instead of the 800 mg Q4W as planned per protocol), the relative dose intensity for this participant is 0.75.

Novartis	For business use only	Page 19 of 46
Statistical Analysis Plan (SAP)		MBG453B12203

Details on the duration in days from the first to last cycle initiated for the derivation of the dose intensity and the relative dose intensity are provided in Appendix Section 4.

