12.3 Treatments

The Safety set will be used for the analyses below. Categorical data will be summarized as frequencies and percentages. For continuous data, mean, standard deviation, median, 25th and 75th percentiles, minimum, and maximum will be presented.

The duration of exposure to study treatment as well as each study treatment component (sabatolimab (mg), venetoclax (mg) and azacitidine (mg)) as well the dose intensity by cycle (mg/day) (derived as the ratio of actual cumulative dose and planned dose intensity per cycle) and the relative dose intensity (%) by cycle (derived as the ratio of dose intensity and planned dose intensity) will be summarized by descriptive statistics.

Concomitant medications and significant non-drug therapies prior to and after the start of the study treatment will be listed and summarized according to the Anatomical Therapeutic Chemical (ATC) classification system.

The number of participants with dose adjustments (reductions, interruptions or permanent discontinuation) for each study treatment component and the reasons will be summarized. All exposure data will be listed.

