The date of first administration of any study treatment component (sabatolimab or azacitidine or venetoclax) is defined as the first date when a non-zero dose of the respective study drug is administered and recorded on the study treatment eCRF page.

Date of last administration of study treatment (sabatolimab or azacitidine or venetoclax)

The date of last administration of any study treatment component (sabatolimab or azacitidine or venetoclax) is defined as the last date when a non-zero dose of the respective study drug is administered and recorded on the study treatment eCRF page. So both, first and last date of study drug, are derived separately for each drug which is part of the study treatment.

Date of first administration of study treatment (combination)

The date of first administration of study treatment (or start date of study treatment) is defined as the first date when a non-zero dose of any component of the study treatment (sabatolimab, Azacitidine or venetoclax) is administered.

Date of last administration of study treatment (combination)

The date of last administration of study treatment (or start date of study treatment) is defined as the last date when the last non-zero dose of any last component of the study treatment (sabatolimab, Azacitidine or venetoclax) is administered.

Date of last exposure to study treatment component (sabatolimab or azacitidine or venetoclax)

One planned cycle length is 28 days and the start date of a cycle is defined as the first administration of azacitidine within a cycle. Azacitidine is planned to be administered daily every cycle during 7 days at the beginning of each cycle (between Day 1 to Day 9). Sabatolimab is administered every 4 weeks (Q4W), on Day 8 of each cycle, unless there was a toxicity leading to a dosing interval increase. Venetoclax is planned to be administered once a day from day 1 to day 14 of the 28-day cycle.

The date of last exposure to sabatolimab is therefore calculated as:

• Minimum (last date of administration of sabatolimab + 27 days, date of death, last contact date in case participant is lost to follow-up), as sabatolimab injections are given Q4W.

The date of last exposure to azacitidine is calculated as:

• Minimum (last date of administration of azacitidine + 20 days, date of death, last contact date in case participant is lost to follow-up) as the 7 doses of azacitidine are given in the beginning of each cycle.

The date of last exposure to venetoclax is calculated as:

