
• Minimum (last date of administration of venetoclax + 14 days, date of death, last contact date in case participant is lost to follow-up) as the 14 doses of venetoclax are given in the beginning of each cycle (in case of regimen change to "one week on, three weeks off" in the last cycle, last date of administration of venetoclax + 21 days will be considered.)

End date of the last cycle initiated

The end date of the last cycle initiated is the maximum date between:

- The planned end date (Day 28) of the last cycle initiated when the last non-zero dose of any last component of the study treatment (sabatolimab or azacitidine or venetoclax) is administered,
- The actual date of the last administration of a non-zero dose of any last component of the study treatment.

The end date of the last cycle initiated (Day 28 or beyond) will be applicable even if this date goes beyond the data cut-off date (i.e., it should not be truncated to the date of data cut-off).

Date of last exposure and duration of exposure to study treatment (combination)

For the calculation of the duration of exposure to study treatment (combination), the date of last exposure to study treatment (combination) will be derived as the minimum date between:

- The latest one of the date of last exposure to any study treatment component (sabatolimab or azacitidine or venetoclax),
- Date of death,
- Last contact date in case participant is lost to follow-up.

The duration of exposure to study treatment (combination) will be calculated as follow: date of last exposure to study treatment (combination) - date of first administration of study treatment (combination) + 1.

Duration from first to last cycle initiated to calculate dose intensity and the relative dose intensity

For the calculation of the dose intensity and relative dose intensity, the duration in days from first to last cycle initiated will be calculated as follow: end date of the last cycle initiated - date of first administration of study treatment (combination) + 1.

Thus, this derivation will be irrespective of date of death or last contact date (i.e., it should not be truncated to the date of death or date of last contact date).

Study day

The study day, describes the day of the event or assessment date, relative to the reference start date (start date of study treatment).

The study day is calculated as follows:

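### SAP 2.4.1.3 labels per-dosing-day doses of azacitidine and venetoclax as planned dose intensities, although intensity is defined per calendar day, and leaves open whether cycle delays lower relative dose intensity

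*SAP*

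**What the plan says.** SAP 2.4.1.3 defines actual dose intensity as "computed as the ratio of actual cumulative dose received and duration in days from first to last cycle initiated". Planned dose intensity "is the ratio of planned cumulative dose and duration in days from first to last cycle initiated". RDI is the first divided by the second.

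The section then lists planned values:

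- Sabatolimab: 400 or 800 mg per 28 days, with no per-day figure. The worked example (an average of 600 mg Q4W against 800 mg, RDI 0.75) is on the cycle scale.
- Azacitidine: 75 mg/m²/day, with 525 mg/m²/28 days given as the same quantity.
- For venetoclax the wording is "the planned dose intensity is 400 mg/day which is equivalent to 5600 mg/28 days", on the stated condition that 400 mg is the recommended full daily dose.

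SAP Section 4 (Appendix) gives the duration for both intensities as "end date of the last cycle initiated - date of first administration of study treatment (combination) + 1". The last cycle is closed at its planned Day 28, or at the last dose if that is later.

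Protocol 12.3 differs. It reports dose intensity by cycle in mg/day, "derived as the ratio of actual cumulative dose and planned dose intensity per cycle", and divides by planned intensity again to obtain RDI.

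**The concern.** There are two gaps in one derivation.

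First, 75 mg/m²/day and 400 mg/day are what a participant takes on a day when the drug is given. The section calls them planned dose intensities and treats them as interchangeable with the 28-day totals. That holds only if a day means a dosing day, and the section counts days differently. Because actual intensity is a dose divided by days, and the protocol reports intensity in mg/day, the per-day figure is the one a programmer might naturally match. Full dosing would then appear as marked under-dosing.

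Second, the definition divides planned cumulative dose by the same observed duration as actual dose, but the SAP never defines planned cumulative dose (2.4.1.2 covers actual dose only). Depending on how it is counted, cycle delays either lower RDI or drop out of it. Delays matter in this regimen: protocol 6.5.3 holds the next cycle for Grade 4 neutropenia or thrombocytopenia in participants in CR or mCR, requires discontinuation only after a delay of more than 28 days, and does not allow sabatolimab dose reductions.

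**Working it through.** **Inputs.** SAP Section 4 gives the schedules: "Azacitidine is planned to be administered daily every cycle during 7 days at the beginning of each cycle" and "Venetoclax is planned to be administered once a day from day 1 to day 14 of the 28-day cycle". The daily doses are 75 mg/m² and 400 mg, and a cycle is 28 days.

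**Step 1: the SAP's 28-day figures.** Dose per dosing day × dosing days:

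- azacitidine 75 × 7 = 525 mg/m²
- venetoclax 400 × 14 = 5600 mg

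Both reproduce exactly.

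**Step 2: the same quantities per calendar day.**

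- azacitidine 525 / 28 = 18.75 mg/m²/day
- venetoclax 5600 / 28 = 200 mg/day

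Read as calendar-day rates, the stated per-day values would imply 75 × 28 = 2100 mg/m² (4 times 525) and 400 × 28 = 11,200 mg (2 times 5600).

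**Step 3: RDI for full doses and no delay.** Over c cycles, actual intensity is (cycle dose × c) / (28 × c), so it does not depend on c.

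| Drug | Actual intensity | RDI, 28-day figure | RDI, stated per-day figure |
|---|---|---|---|
| Azacitidine | 18.75 mg/m²/day | 18.75 / 18.75 = 100% | 18.75 / 75 = 25% |
| Venetoclax | 200 mg/day | 200 / 200 = 100% | 200 / 400 = 50% |

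**Step 4: RDI for full doses with delayed cycles.**

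- If planned cumulative dose is counted per cycle started, actual and planned doses are equal and share the same duration. RDI is 100% whatever the delay.
- If planned dose accrues at the fixed 28-day rate, RDI = 28 / cycle length: 28/35 = 80% for 35-day cycles and 28/42 = 67% for 42-day cycles.
- Because an undelayed last cycle closes at Day 28, six cycles of which the first five last 42 days span 5 × 42 + 28 = 238 days. The fixed-rate RDI is then (6 × 28)/238 = 168/238 = 71%.

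**Step 5: inhibitor-related venetoclax doses.** Protocol Table 6-2 lists 70, 100 and 200 mg with CYP3A or P-gp inhibitors. Protocol 6.5.1.3 counts such participants as having received the planned dose for DLT evaluability. Against an unconditional 200 mg/day, a participant taking 70 mg on all 14 days has actual intensity 70 × 14 / 28 = 35 mg/day and RDI 35/200 = 17.5%. The SAP's condition on the full daily dose therefore has to stay.

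**Step 6: protocol 12.3.** Cumulative mg divided by an intensity in mg/day gives days; divided by a planned amount in mg per cycle it gives a pure ratio. Neither gives the stated mg/day.

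**The case against.** The strongest reply is that the SAP already settles the denominator. Its definition of planned intensity, the calendar-day duration in Section 4, the 28-day figures and the sabatolimab example all lead to 100% for full, undelayed dosing. The equivalence is exact per dosing day, and the venetoclax bullet itself identifies 400 mg as a daily dose. This stands: 25% and 50% arise only if someone uses the mislabelled figure against the definition. A reader might infer that the SAP prescribes two rival planned intensities, or that full dosing will be reported as 25% or 50%. The documents support neither.

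On delays, the defining sentence leads straight into the 28-day bullets, so planned dose can be read as accruing at those rates. Sentence and bullets then agree on about 67% for 42-day cycles. That is a reasonable reading, but it is not written down, and the sabatolimab example involves no delay that would settle it. Duration of interruptions and number of cycles initiated are summarized separately (SAP 2.4.1.4 and 2.4.1.5), so dosing gaps would not rest on RDI alone.

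On protocol 12.3, one might compute 5600/200 = 28 and then 28/200 = 0.14 for full-dose venetoclax. That takes planned intensity as 200 mg/day; with 5600 mg per cycle the first ratio is 1. The value 0.14 is not an expected output. Only the failure of units is firm, and the SAP's own formula already avoids it.

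On impact, dose intensity and RDI are on the list for the safety review meetings (SAP 2.8), which might suggest that dose decisions were at risk. The SAP reports the second review as held on 26-Sep-2022 and plans none after the run-in. The Bayesian assessment uses DLTs, and evaluability uses dose counts (11 of 14 and 21 of 28), not RDI. The documents do not say which denominator those review tables used.

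**Conclusion.** The point holds as a unit and definition defect. Two values labelled as planned dose intensities do not fit the section's calendar-day definition: azacitidine is 4-fold too high and venetoclax 2-fold. If used as denominators, they would turn a true RDI of 100% into 25% and 50%. These figures assume full doses in undelayed 28-day cycles and the 400 mg full daily dose of venetoclax.

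The treatment of delays is open rather than wrong. The contrast of 100% with about 67% in 42-day cycles depends entirely on how the undefined planned cumulative dose is counted.

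The consequence is confined to descriptive exposure tables in an abbreviated CSR for the run-in, planned at about 18 participants. DLT incidence, the Bayesian toxicity assessment and the CR rate are unaffected. It is worth correcting because it takes only wording and the exposure tables would otherwise depend on a programmer's reading.

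**What to change.** In SAP 2.4.1.3:

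- State planned intensities per calendar day on the 28-day cycle: sabatolimab 400/28 or 800/28 mg/day, azacitidine 18.75 mg/m²/day, and venetoclax 200 mg/day when the recommended full daily dose is 400 mg. Keep that condition, and scale the planned venetoclax value for the inhibitor-related reductions in protocol Table 6-2, in line with how protocol 6.5.1.3 treats those participants for evaluability.
- Label 75 mg/m²/day and 400 mg/day as per dosing day, or delete them.
- Define planned cumulative dose as accruing at the 28-day rate over the observed duration, so that delays lower RDI.

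In SAP Section 3, record that this derivation replaces the protocol 12.3 formula, whose units do not give mg/day.

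The cost is SAP wording and one derivation in the exposure program. No new data are needed.

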2.4.1.4 Dose reduction, dose interruption and permanent discontinuations

The number (%) of participants with any dose changes (incl. reductions, interruptions, or permanent discontinuations) and the reasons (e.g. AE, dosing error, dispensing error) will be taken from the 'Study Treatment eCRF' and summarized by study treatment component. The total duration of interruptions by participant will be summarized for the study population by time intervals, e.g. < 1week, $\geq 1 -< 2$ weeks, $\geq 2 -< 3$ week etc. (these time intervals may be adjusted depending on the observed data).

2.4.1.5 Cycle initiated

The number of cycles initiated by participant will be summarized.

2.4.2 Prior, concomitant and post therapies / HSCT

Concomitant medications and significant non-drug therapies prior to and after the start of the study treatment will be summarized according to the Anatomical Therapeutic Chemical (ATC) classification system.

Prior anti-neoplastic medications will be summarized using the FAS. Medications will be summarized by ATC class and preferred term.

Anti-neoplastic medications after discontinuation of study treatment during follow-up within the study will be summarized using the FAS by ATC class and preferred term. All HSCTs will be listed.

Transfusions of blood products (including those not related to MDS) prior and after start of study treatment will be listed. Only MDS related transfusions (e.g. bleeding, surgical procedure, hemolysis, infections) of platelets and red blood cells will be summarized using the FAS. For that, the number of transfusion units will be normalized by time (i.e. fixed 8 week interval, mentioned below as episode) prior to and on-treatment. The number of participants with at least one transfusion episode, the number of transfusion episode per participant and the number of units per episode will also be described. Further analyses to summarize transfusion independence are described in the efficacy section.

2.5 Analysis of the primary objectives

The primary objective of the Safety run-in (Part 1) of the study is to determine whether sabatolimab 400 mg and 800 mg are safe (i.e. not meeting overdose criteria) when added in combination with azacitidine and venetoclax.

The primary objective of the Expansion (Part 2) is to determine the complete remission rate (CR) of sabatolimab (800 mg Q4W) in combination with azacitidine and venetoclax. This analysis will include all participants' data from cohort 2 of the Safety run-in (Part 1) and Expansion (Part 2).

2.5.1 Primary endpoints and estimand

2.5.1.1 Safety run-in (Part 1)

For the Safety run-in part, the primary endpoint is the incidence of DLTs during the first 2 cycles of treatment for participants in the DDS. The number and percentage of DLTs occurring during the DLT evaluation period will be summarized by system organ class and preferred term in the DDS, and the DLTs will be listed

Details on the definition of DLT which are to be captured in the Adverse Event eCRF were defined as described in (Table 6-4 of study protocol).

2.5.1.2 Cohort 2 of Safety run-in (Part 1) and Expansion (Part 2)

The primary endpoint is the proportion of participants included in the FAS and assigned to sabatolimab at the 800 mg Q4W dose level (in both safety run-in and expansion parts) who achieved a complete remission (CR) as per investigator assessment.

Response assessment rules

Response assessment will be performed by the investigator according to the assessment schedule depicted in protocol Table 8-1 based on available bone marrow assessment (C3D1, C7D1, C10D1, C13D1 and then C19D1, C25D1 and then every 12 cycles), hematology data (at D1, D8, D22 of the first 2 cycles and then D1 and D8 of each cycle until end of treatment and then every 12 weeks) and all transfusions records as detailed in s using the modified version of the published response criteria IWG for MDS. Moreover, response assessments can be performed at any time if clinically indicated, e.g. for confirmation of response but also for any suspicion of progression/relapse. These assessments are recorded as an unscheduled visit in the eCRFs and will be considered for the overall determination of response and progression/relapse with the respective assessment date.

The investigator does not determine best overall response, he/she is assessing only the response based on the given bone marrow and peripheral blood data, the history of transfusions and myeloid growth factor received within the last 2 weeks.

The best overall response (BOR) will be derived based on the CR primary endpoint rules by Novartis as below:

- CR = at least one determination of CR without progression or relapse from CR within the four weeks after CR
- mCR = at least one determination of mCR (and not qualifying for a CR).
- PR = at least one determination of PR (and not qualifying for a CR, mCR).
- HI = at least one determination of HI (and not qualifying for a CR, mCR, PR)
- SD = at least one SD assessment and not qualifying for CR, mCR, PR or HI).
- PD = progression after start of treatment and not qualifying for CR, mCR, PR, HI or SD.
- UNK = all other cases (i.e., not qualifying for confirmed CR or mCR or PR or HI and without SD or progression).

Details for the definition of response categories (captured in the eCRF by the Investigator) as defined in Table 8-2 of the protocol, are described in Table 2-2 below.

Response category	Definition [#]	
Complete remission (CR)	Bone marrow:	
	<= 5% blasts with normal maturation of all cell lineages. (Note: Persistence of dysplasia will be noted but does not preclude achievement of complete remission [CR])	
	Peripheral blood:	
	1. Hgb $\geq 10 \text{ g/dl}$ AND	
	2. Platelets $\geq 100*10^9$ /L AND	
	3. Neutrophils $\geq 1.0*10^9$ /L AND	
	4. Blasts 0%	
	(Note: the participant must not receive RBC or platelet transfusions, myeloid growth factor within 2 weeks before this disease assessment)	
marrow Complete remission (mCR)	Bone marrow:	
	<= 5% blasts and blast count decrease by \geq 50% compared to baseline	
	Peripheral blood/transfusion: Marrow CR may be achieved with or without improved blood counts or with or without transfusions	
Partial remission (PR)	All CR criteria except	
	Bone marrow: $\geq 50\%$ decrease from baseline in blasts in bone marrow AND blast count in bone marrow $> 5\%$	
Stable Disease (SD)	Failure to achieve at least PR, but no evidence of progression for >8 weeks	
Relapse from CR	Only in participants with a CR	
	At least 1 of the following criteria is met: [in absence of another explanation not due to MDS, such as acute infection, bleeding, hemolysis, etc. Note that observation of peripheral blasts is not a sufficient criterion for relapse. However, in that case, a bone marrow examination should be made to determine whether relapse has occurred]	

Table 2-2Modified response classification per IWG-MDS criteria (Platzbecker et
al 2019, Cheson et al 2006, Cheson et al 2000)

	1. Return to baseline bone marrow blast percentage	
	2. Decrease of \geq 50% from maximum remission/response*** levels in neutrophils AND neutrophils <1.0*10 ⁹ /L. Note: neutrophils counts during periods of active infection will not be considered in determining the maximum	
	3. Decrease of \geq 50% from maximum remission/response*** levels in platelets AND platelets < $100*10^9/L$	
	4. Decrease from maximum remission/response*** levels in Hgb concentration by ≥ 1.5 g/dL AND Hgb < 10 g/dL	
	5. Becoming transfusion dependent**	
Disease progression	At least 1 of the following criteria is met:	
	[in absence of another explanation not due to MDS, such as acute infection, bleeding, hemolysis, etc. Note that observation of peripheral blasts is not a sufficient criterion for progression. However, in that case, a bone marrow examination should be made to determine whether relapse has occurred]	
	Bone marrow according to the number of blasts of the participant at baseline:	
	1. Less than 5% blasts at baseline : \geq 50% increase in blasts over baseline to > 5% blasts	
	2. 5% - < 10% blasts at baseline : \geq 50% increase over baseline to > 10% blasts	
	3. 10% - < 20% blasts at baseline : \geq 50% increase over baseline to > 20% blasts.	
	Participants with more than 20% of blasts will be considered to have transformation to acute leukemia per 2016 WHO classification (Arber et al, 2016)	
	Peripheral blood:	
	1. Decrease of \geq 50% from maximum remission/response*** levels in neutrophils	

AND neutrophils $< 1.0*10^{9}/L$. Note: neutrophils counts during periods of active infection will not be considered in determining the maximum
2. Decrease of \geq 50% from maximum remission/response*** levels in platelets AND platelets < $100*10^{9}/L$
3. Reduction from maximum remission/response *** levels in Hgb by $\geq 2g/dL \text{ AND } Hgb < 10g/dL$
Becoming transfusion dependent**
Occurrence of acute leukemia, or extramedullary leukemia per investigator's judgement

Modified Hematologic Improvement per IWG-MDS criteria (Cheson et al 2006)

HI category	Definition [#] (HI must last at least 8 weeks)	
Erythroid response (HI-E) (pretreatment*, <11 g/dL)	1. Hgb increase from baseline by \geq 1.5 g/dL, in at least 2 consecutive Hgb measurements and maintained over at least 8 weeks	
	2. Relevant reduction from baseline of units of RBC transfusions by an absolute number of at least 4 RBC transfusions/8 weeks compared with the pre-treatment transfusion number in the previous 8 weeks. Only RBC transfusions given for a Hgb of < 9 g/dL pre- treatment will count in the RBC transfusion response evaluation.	
Platelet response (HI-P) (pretreatment*, <100 x 10 ⁹ /L)	1. Absolute increase from baseline of \geq 30 x 10 ⁹ /L for participants starting with $>$ 20 x 10 ⁹ /L platelets	
	2. Increase from baseline from $< 20 \times 10^9/L$ to $> 20 \times 10^9/L$ and by at least 100% for participants starting with $< 20 \times 10^9/L$ platelets	
Neutrophil response (HI-N) (pretreatment*, <1.0 x 10 ⁹ /L)	At least 100% increase and an absolute increase from baseline of $> 0.5 \times 10^9/L$	
[#] If not defined otherwise, all of the criteria ap	ply. Words that are written in italics highlights	

"If not defined otherwise, all of the criteria apply. Words that are written in italics highlights the modifications from the IWG criteria described in the reference publications.

*Pretreatment counts correspond to the baseline (not influenced by transfusions)

**Definition of transfusion dependence and independence for red blood cells (RBC) and/or platelets are described below.

***maximum remission/response levels correspond to the best values reported in post baseline.

Transfusions Status Definitions for RBC/platelets

Transfusions for intercurrent diseases not due to study indication (e.g. bleeding, surgical procedure, hemolysis, infections) should not be taken into account for the following:

Transfusion dependence:

1. At baseline: participants having received ≥ 3 units of transfusion within the 8 consecutiveweekspriorto2. Post-baseline: participants having received ≥ 3 units of transfusion within any 8consecutive weeks during the course of the study

Transfusion independence:

1. At baseline: participants having received 0 units of transfusion within the 8 consecutive weeks prior to baseline.

2. Post-baseline: participants having received 0 units of transfusion within any 8 consecutive weeks during the course of the study.

Primary estimand

The primary clinical question of interest is the following:

Is sabatolimab 800 mg Q4W in combination with fixed doses of azacitidine (75 mg/m² Day 1-7) and venetoclax (400 mg Day 1-14) associated with improved efficacy (i.e. CR rate $\geq 50\%$) for participants with high or very high risk MDS?

The primary endpoint (combining data from cohort 2 of the Safety run-in (Part 1) and the Expansion (Part 2) (i.e. sabatolimab 800 mg (Q4W)) is the proportion of participants achieving a complete remission (CR) as per investigator assessment.

The primary efficacy estimand is described by the following five attributes:

- **Population:** Adult participants as described by inclusion/exclusion criteria not eligible for intensive chemotherapy nor for HSCT with high or very high risk MDS (IPSS-R criteria) (Greenberg et al 2012) as per inclusion/exclusion criteria and as assessed locally by the investigator.
- Variable: Best overall response among all disease response assessments as assessed by investigator per modified IWG MDS criteria (Cheson et al 2006) up to new anti-cancer therapy (including HSCT).
- **Treatment:** Study treatment initiates sabatolimab 800 mg Q4W + azacitidine (75 mg/m² Day 1-7) + venetoclax (400 mg Day 1-14). Participants will continue treatment

until a reason of treatment discontinuation is met (e.g. progression, unacceptable toxicity, HSCT).

- Intercurrent events:
 - **Study treatment modification:** all CR will be taken into account regardless of any study treatment component interruption, dose adjustment or permanent discontinuation.
 - **Concomitant medications and supportive care:** A participant may receive blood transfusion as supportive care and prophylactic treatment as clinically indicated (e.g. antiemetics, antibiotics, antifungals). All CR will be taken into account regardless of any concomitant medication administration including prohibited medications.
 - New anti-cancer therapy/HSCT: CR achieved after initiation of a new anti-cancer therapy or HSCT will not be taken into account.
- Summary measures: The CR rate and the 95% confidence interval (CI).

